1.0 Abbreviations and Definitions

APACHE II = Acute Physiology and Chronic Health Evaluation, version 2
BIDMC = Beth Israel Deaconess Medical Center
CVP = Central venous pressure
ECMO = Extracorporeal Membrane Oxygenation
ER = Emergency Room
GVEC = Graded Volume Expansion Challenge
ICU = Intensive Care Unit
IMC = Intermountain Medical Center
ITT = Intention to Treat
LAR = Legally Authorized Representative
OFFD = Organ-Failure-Free Days at 28 days
P/F = PaO₂/FiO₂ ratio
SAE = Serious Adverse Event
ScvO₂ = Central venous oxygen saturation
SMC = Safety Monitoring Committee
SOFA = Sequential Organ Failure Assessment score
SUSAR = Serious and Unexpected Suspected Adverse Reaction

Definitions

Adverse Event: Any untoward medical occurrence associated with the use of a drug or study procedure, whether or not considered drug related. (cf. 21 CFR 312.32(a))

Adverse reaction: An adverse reaction means any adverse event caused by a drug. Adverse reactions are a subset of all suspected adverse reactions where there is a reason to conclude that the drug caused the event.

Intention to Treat (ITT): All eligible and consented patients who undergo esmolol infusion will be included in the ITT cohort for the purposes of analyzing the primary and secondary study outcomes.

Legally Authorized Representative: An individual, judicial, or other body authorized under applicable law to consent on behalf of a prospective patient to the patient's participation in the clinical study.

Life-threatening adverse event or life-threatening suspected adverse reaction: An adverse event or suspected adverse reaction is considered "life-threatening" if, in the view of the investigator, its occurrence places the patient or subject at immediate risk of death. It does not include an adverse event or suspected adverse reaction that, had it occurred in a more severe form, might have caused death. (cf. 21 CFR 312.32(a))

Organ-failure-free days: As of day 28, the number of calendar days on which the patient receives none of (a) vasopressor therapy, (b) mechanical ventilation, or (c) renal replacement therapy. If the patient dies on or before day 28, they have -1 organ-failure-free days.

Serious adverse event (SAE) or serious suspected adverse reaction or serious unexpected suspected adverse event (SUSAR). An adverse event or suspected adverse reaction is considered "serious" if, in the view of the investigator, it results in any of the following outcomes: Death, a life-threatening adverse event, inpatient hospitalization or prolongation of existing hospitalization, a persistent or significant incapacity or substantial disruption of the ability to conduct normal life functions, or a congenital anomaly/birth defect. Important medical events that may not result in death, be life-threatening, or require hospitalization may be considered serious when, based upon appropriate medical judgment, they may jeopardize the patient or subject and may

require medical or surgical intervention to prevent one of the outcomes listed in this definition. (cf. 21 CFR 312.32(a))

Study Day: The first day of esmolol infusion is study day zero. The next day is study day one, and so on etc.

Study Drug: Esmolol infusion for septic shock patients with persistent tachycardia after adequate volume expansion.

Study hospital: Defined as the hospital where the patient is enrolled.

Study withdrawal: Defined as permanent withdrawal from the study before the completion of study activities. This does not include those subjects who have completed the esmolol infusion. If a patient or surrogate requests to withdraw from the study, investigators should seek explicit permission to continue data collection for relevant outcomes.

Suspected adverse reaction: any adverse event for which there is a reasonable possibility that the drug caused the adverse event. Reasonable possibility means that there is evidence to suggest a causal relationship between the drug and the adverse event. A suspected adverse reaction implies a lesser degree of certainty about causality than an adverse reaction, as per 21 CFR 312.32(a).

Unexpected adverse event or unexpected suspected adverse reaction. An adverse event or suspected adverse reaction is considered "unexpected" if it is not listed in the investigator brochure (or package insert) or is not listed at the specificity or severity that has been observed. "Unexpected," as used in this definition, also refers to adverse events or suspected adverse reactions that are mentioned in the investigator brochure or package insert as occurring with a class of drugs or as anticipated from the pharmacological properties of the drug, but are not specifically mentioned as occurring with the particular drug under investigation. (cf. 21 CFR 312.32(a))

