2.0 Study Summary

2.1 **Title:** Esmolol to Control Adrenergic Storm in Septic Shock (ECASSS) – ROLL-IN

2.2 **Objective:** To evaluate the adequacy and efficiency of study protocols for the main ECASSS study.

2.4 **Study design:** Prospective, single arm, feasibility (“roll-in”) study of esmolol infusion in septic shock.

1. **Inclusions.** We will include patients admitted to the ICU for sepsis who are within 48 hours of septic shock and ICU admission and are simultaneously tachycardic (heart rate >90/min) **and** on vasopressors for > 60 min. Patients must meet criteria at the time of enrollment.
2. **Final safety check.** After enrollment and before esmolol infusion, ScvO₂, transthoracic echocardiogram, evaluation of fluid responsiveness, and review of telemetry/EKGs will occur to assure that no exclusion criteria are present.
 - a. If no exclusion criteria are present, patients will start esmolol infusion
 - b. If patient is still fluid responsive but otherwise has no exclusions, fluid will be administered by explicit protocol until no longer fluid responsive, and then the patient will receive esmolol infusion. If tachycardia has resolved as a result of volume expansion, esmolol infusion will not occur until tachycardia and vasopressor administration co-occur. After esmolol infusion, volume expansion will be managed as part of the esmolol titration protocol.
 - c. Patients who fail the final safety check will NOT start esmolol infusion but will be followed for non-interventional aims (e.g., serial TTEs, vascular biomarkers) to understand better the natural history of cardiogenic shock superimposed on septic shock.
3. **Esmolol infusion**
 - a. Esmolol infusion, started without bolus, with slow upward titration to a maximum infusion rate is protocolized (see protocol in Appendix 1), with a target heart rate of 80-90/min.
 - b. Esmolol infusion will be stopped in the event that cardiogenic shock, excessive bradycardia, grade 2 or grade 3 heart block, or hypotension, or bronchospasm occur, as per protocol.
4. **Other care**
 - a. ICU patients are managed according to current Surviving Sepsis campaign guidelines as per usual practice.

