2.6 Exclusion criteria

1. Lack of informed consent.
2. Currently receiving ECMO.
3. Known pregnancy or nursing.
4. Patient is a prisoner.
5. Patient on hospice (or equivalent comfort care approach) at or before the time of enrollment.
6. Known or current atrial fibrillation.
7. Previously enrolled in the trial.
8. Known allergy to esmolol or vehicle (see Appendix 2 for BREVIBLOC vehicle ingredients).
9. Receipt of nodal blocking agents (see Appendix 3 for list of such agents) within three half lives
10. Hemoglobin $<$ 7 gm/dl.
11. Cardiac arrest within 24 hours.
12. Pulmonary hypertension (moderate or severe), from documented history of prior right heart catheterization or current evidence on TTE of **any** of the following
 - mPAP \geq 35mmHg

- SPAP \geq 60mmHg
13. Cardiovascular collapse, as manifested by inability to achieve a MAP of 65 mmHg with vasopressor therapy.
 14. Cardiogenic shock, as defined by **any** of the following
 - Cardiac index \leq 2 L/min/m²
 - Ejection fraction \leq 25%
 - ScvO₂ \leq 60%
 - Current infusion of any dose of dobutamine, milrinone, or dopamine
 - Current infusion of epinephrine for clinically diagnosed cardiogenic shock
 15. Significant atrioventricular dysfunction
 - Sick sinus syndrome
 - PR interval > 200 msec
 - Current evidence or prior history of Grade 2 or Grade 3 heart block
 - Pacemaker or plans to place a pacemaker
 16. Pheochromocytoma or status asthmaticus
 17. Receiving clonidine, guanfacine, or moxonidine
 18. Hemoglobin < 7 gm/dl
 19. Cardiovascular collapse (failure to achieve MAP of 65mmHg)
 20. Cardiac arrest within 24 hours
 21. Worse than moderate aortic stenosis
 - Known aortic stenosis, with any of (1) mean gradient \geq 40 mmHg OR (2) maximum gradient \geq 60mmHg OR (3) aortic valve area \leq 1.0cm² OR (4) aortic valve area index \leq 0.85cm²/m² body surface area.
 22. Worse than mild mitral stenosis
 - Known mitral stenosis, with any of (1) valve area \leq 1.5 cm² OR mean gradient \geq 5 mmHg.

2.7 Sample size: The study will enroll up to 10 patients at 1 center.

2.8 Non-clinical outcomes for ROLL-IN:

1. Proportion of eligible patients consented
2. Proportion of compliance with final safety check
 - a. Protocol compliance is considered adequate where compliance is 100% for the safety check.
3. Proportion of protocol compliance

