5.1.1.1 Review for final exclusions

A study investigator will review, with the research coordinator, all study inclusions and exclusions before consent and enrollment. After enrollment, according to the protocol depicted in FIGURE 2, study personnel will confirm that cardiogenic shock is absent and adequate volume expansion has occurred. These evaluations are performed after consent because they involve study procedures, which cannot be required of subjects who have not consented. If cardiogenic shock is documented at this point, a subject will be followed for outcomes and biomarkers but esmolol will *not* be infused. After the final safety check has been completed and the patient is confirmed eligible for study drug infusion, study drug infusion should be started as soon as possible and within 3 hours of passing the final safety check.

[figure not shown]

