7.0 Statistical plan

7.1 Statistical Analysis

The primary comparison is between treatment assignment and organ-failure-free days at 28 days. Secondary analyses are the evaluation of adequacy of screening, enrollment, and study protocols.

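### The outcome cohort is limited to eligible infused patients, so a patient given esmolol in error could be missing from the planned outcome summaries

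*Combined protocol and SAP*

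**What the plan says.** The definition of Intention to Treat in Section 1.0 reads: "All eligible and consented patients who undergo esmolol infusion will be included in the ITT cohort". The definition assigns this cohort to both the primary and the secondary outcomes. Eligibility, consent and infusion are three separate conditions. No all-treated set is defined anywhere, and no rule covers a patient who is infused and later found ineligible.

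*Eligible* is not defined for this purpose. Section 5.1.1.1 uses the word prospectively: "After the final safety check has been completed and the patient is confirmed eligible for study drug infusion", infusion should follow promptly. The check itself (Section 2.4, item 2) consists of ScvO2, echocardiogram, an assessment of fluid responsiveness, and a rhythm review: "review of telemetry/EKGs will occur to assure that no exclusion criteria are present". On the other outcome of the check, the same item says: "Patients who fail the final safety check will NOT start esmolol infusion but will be followed for non-interventional aims".

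Section 2.7 sets the size: "The study will enroll up to 10 patients at 1 center". Section 2.8, item 2a, sets the criterion for the check: "Protocol compliance is considered adequate where compliance is 100% for the safety check". It names no denominator. Section 7.1 makes organ-failure-free days the primary comparison and adds: "Secondary analyses are the evaluation of adequacy of screening, enrollment, and study protocols".

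**The concern.** The roll-in is meant to show how the procedures perform in practice, including when they go wrong. A cohort that requires eligibility as well as infusion removes an infused patient because of a protocol error, after that patient has been exposed to the drug. The removal is unlikely to be neutral. Section 4.3 explains that the exclusions are mainly there to keep out patients who might not tolerate beta-blockade, so a patient infused despite one is plausibly at higher risk than the rest.

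Such an error is foreseeable. Section 2.6 excludes recent nodal blockers and current clonidine, guanfacine or moxonidine. These are matters of medication history, which none of the tests in the final check would reveal, and they can come to light after infusion has begun. In an open-label, single-arm study, whether that patient counts should not be left open until the outcome is known.

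The summaries at stake are those in Sections 2.8.1 and 2.8.2: organ-failure-free days, mortality to day 90, cardiogenic shock through day 14, and second- or third-degree heart block. Section 7.2 says the roll-in data will support a larger trial, and Section 7.3 plans an analysis of the experience at two centers.

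**Working it through.** The plan gives no power calculation and no error rate, so there is no stated figure to reproduce. The check compares each summary in all infused patients with the same summary in eligible infused patients only.

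**Inputs from the documents.** Up to 10 patients (Section 2.7); death on or before day 28 scores -1 organ-failure-free days (Section 1.0); 100% criterion for the safety check (Section 2.8, item 2a).

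**Assumptions.** All 10 patients are infused and exactly one is ineligible. The event counts, the mean for the other nine patients and the error rate are illustrative.

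**1. Which patient is dropped under each reading of *eligible*.**
- Eligible in fact: a patient infused despite a missed exclusion is dropped.
- Confirmed eligible at the check, as in Section 5.1.1.1: a patient with a missed history-based exclusion stays in, but one infused without completing or passing the check is dropped.

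Each reading removes some infused patient because of an error, and the text does not choose between them.

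**2. Event proportions** (exact 95% intervals).
- That patient has the only event: 1/10 = 10% (0.3% to 44.5%) becomes 0/9 = 0% (0% to 33.6%).
- Three deaths, one of them in that patient: 3/10 = 30% becomes 2/9 = 22.2%.

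**3. Mean organ-failure-free days.** If that patient dies (-1) and the other nine average m, the mean in all infused patients is (9m - 1)/10. Dropping the patient raises it by m - (9m - 1)/10 = (m + 1)/10.

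| m (assumed) | All 10 | Eligible 9 | Rise |
|---|---|---|---|
| 5 | 4.4 | 5 | 0.6 |
| 10 | 8.9 | 10 | 1.1 |
| 15 | 13.4 | 15 | 1.6 |
| 20 | 17.9 | 20 | 2.1 |

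**4. Chance that the situation arises.** With per-patient probability p of an ineligible infusion, the chance of at least one in 10 is 1 - (1 - p)^10. For assumed p of 2%, 5% and 10% this is 18%, 40% and 65%.

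**5. Safety-check criterion, conditional.** If the error was a failure of the check itself, compliance is 9/10 = 90% in all infused patients, which misses the criterion. It would be 9/9 = 100% only if the eligible cohort were the denominator.

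**The case against.** **Safety capture.** A reader might infer that the patient disappears from every outcome and that harm is hidden. The documents do not support that. Under Section 6.2 the SMC sees all study data with a narrative for each patient, and every death during infusion is reported within 24 hours. Section 10.2 collects serious adverse events during infusion and for 24 hours afterwards, whatever the suspected cause. Section 10.1 collects events leading to permanent discontinuation and reports STOP events separately. Appendix 4 has the SMC review adverse events and clinical outcomes at its interim looks, and A4.2 treats third-degree heart block on esmolol as drug-related without adjudication. None of this depends on cohort membership. The channel does have limits. The scheduled reviews fall at 3 and 6 patients. A4.3 generally exempts study outcomes from adverse event reporting, including death not related to the drug or procedures and cardiogenic shock that persists 20 minutes after esmolol stops. For later or exempt events the outcome summaries matter more, so this objection narrows the point without removing it.

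**The 100% criterion.** A reader might also infer that the definition turns a failed safety-check result into a pass. The plan does not say so. The criterion is listed among the non-clinical outcomes and has no denominator. Section 7.1 calls protocol adequacy a secondary analysis, which is only a loose link to the cohort. An infused-only denominator also fits poorly, because a patient correctly stopped at the check is a compliance success who is never infused. Nor is every missed exclusion a failed check: it can be carried out in full while a recent nodal blocker goes unnoticed, leaving compliance at 10/10. This objection stands, and the reversal is no more than a conditional possibility.

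**The prospective reading.** Section 5.1.1 has an investigator review all criteria before consent, and no section provides for later adjudication of eligibility. On that view most missed exclusions stay in. This reduces the problem, but step 1 of the working shows that it does not end it.

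**Recording of errors.** Section 5.1.5 lists the incidence of protocol violations, so an ineligible infusion should be documented. That records the error; it does not restore the patient to the outcome summaries.

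**Conclusion.** The concern holds as a point about the planned summaries of clinical outcomes. Read literally, the definition leaves out a patient infused in error, the likely direction is towards better-looking results, and no all-treated set is there to correct it. One patient can change 1/10 to 0/9, or raise mean organ-failure-free days by 0.6 to 2.1 under the assumed means.

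This rests on at least one ineligible infusion occurring, on that patient having a poor outcome, and on *eligible* being applied so as to remove the patient. The intervals for 1/10 and 0/9 overlap widely, and the study tests no hypothesis against a control. What changes is the description: one event or none. It is a low-cost clarification to consider.

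**What to change.** - Delete *eligible* from the definition in Section 1.0. Analyse clinical outcomes in all consented patients who received any esmolol, whatever is later found about eligibility.
- Call this the treated set. A set conditional on infusion is not an intention-to-treat set, and deleting the one word does not make it so.
- List ineligible infusions as protocol deviations, and show an eligible-only summary as a sensitivity listing.
- State in Section 2.8, item 2, that safety-check compliance is scored in all enrolled patients due the check, including those who are then not infused. The first change does not supply this denominator, so it needs its own sentence.

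The cost is a few words and one extra listing. Outcomes may look slightly worse if an ineligible patient was infused.

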 - a. For the esmolol titration protocol, each hour (the closest value of heart rate to the hour) during the esmolol infusion will be determined to be “in range” or “out of range,” with 3bpm margin for compliance (i.e., heart rate 77 to 93bpm). The initiation and cessation of esmolol will also be included as a timepoint for evaluation of compliance. Protocol compliance is considered adequate where overall compliance on hourly checks is >80%.
 - b. For STOP events, protocol compliance is considered adequate at 100%.
 - i. 30min moving average of cardiac index below threshold
 - ii. 30min moving average of norepinephrine infusion rate above threshold
 - iii. Clinician determines that shock has substantially worsened on esmolol.

- c. For VOLUME EXPANSION events, protocol compliance is considered adequate at 90%.
- 4. Amount of research coordinator time spent on different tasks

2.8.1 Anticipated primary clinical outcome for main trial (this will also be recorded for ROLLIN): Organ-failure-free days at 28 days. An organ-failure-free day is defined as a calendar day on which the patient receives none of (a) vasopressor therapy, (b) mechanical ventilation, or (c) renal replacement therapy.

2.8.2 Anticipated secondary clinical outcomes for main trial (these will also be recorded for ROLLIN):

1. All-cause hospital mortality
2. All-cause 28-day and 90-day mortality
 - a. Mortality will be ascertained through telephone followup for patients who were discharged alive before 90 days.
3. Peak serum high-sensitivity troponin
 - a. Troponin will be measured on day 0 and day 1.
4. LV global longitudinal strain at 24 hours
5. Time to transition to quiescent vascular phenotype, as defined by serum Angpt-2 level < 1ng/ml.
6. ICU-free days to day 28
 - a. Patients who die before 28 days will be assigned -1 ICU-free days, using a methodology similar to that used for organ-failure-free days.
7. Cardiogenic shock/requirement for inotropes through day 14. This is a binary variable and is met when any of the following is present
 - a. Dobutamine or milrinone infusion at any dose, lasting > 60min
 - b. $CI \leq 2$ L/min/m² lasting > 30 min on NICOM
 - c. $ScvO_2 \leq 60\%$ on any measurement
8. Development of second or third degree heart block.

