3.3 Objective

To assess the adequacy of subject identification and enrollment procedures. To assess the adequacy and efficiency of study protocols. To evaluate the estimates of coordinator burden for screening and enrollment.

3.5.1 Non-clinical outcomes for ROLL-IN:

1. Proportion of eligible patients consented
2. Proportion of protocol compliance
3. Amount of research coordinator time spent on different tasks

3.5.2 Anticipated primary clinical outcome for main trial: Organ-failure-free days at 28 days. Defined as the number of calendar days on which the patient receives none of (a) vasopressor therapy, (b) mechanical ventilation, or (c) renal replacement therapy. (Patients who die before 28 days will be assigned -1 organ-failure-free days in order to avoid making death equivalent to prolonged organ dysfunction.) For example, a patient who died on day 12 would have -1 organ-failure-free days, while a patient who resolved all organ dysfunction on day 9 but died on day 30 would be categorized as having 19 organ-failure-free days.

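### Organ-failure-free days have no rule for days between dialysis sessions, so unresolved kidney failure can score as free; separately, a death on day 28 is scored two ways

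*Combined protocol and SAP*

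**What the plan says.** The outcome is defined three times, each time by what the patient received on a given calendar day.

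- Section 1.0: "the number of calendar days on which the patient receives none of" the three listed supports, as of day 28. Renal replacement therapy is the third support, with no modality named.
- Section 2.8.1: "An organ-failure-free day is defined as a calendar day on which the patient receives none of (a) vasopressor therapy" or either of the other two supports.
- Section 3.5.2: "Defined as the number of calendar days on which the patient receives none of (a) vasopressor therapy" or either of the other two, followed by an example in which "a patient who resolved all organ dysfunction on day 9 but died on day 30 would be categorized as having 19 organ-failure-free days".

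None of the three says how to treat a day that falls between two dialysis sessions. The exclusion lists (2.6 and 4.3.1) do not exclude patients already on chronic dialysis.

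The death rule also differs. Section 1.0 gives -1 with the condition "If the patient dies on or before day 28". Section 3.5.2 says "Patients who die before 28 days will be assigned -1 organ-failure-free days". Section 2.8.1 states no death rule. For ICU-free days, 2.8.2 and 3.5.3 use the same cut-off as 3.5.2.

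Section 7.1 names this outcome as the primary comparison. Sections 2.8.1 and 3.5.2 present it as the anticipated primary outcome of the main trial, and 2.8.1 adds that it is also recorded here.

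**The concern.** Vasopressors and ventilation are usually given in continuous runs, so scoring by daily receipt follows the course of the organ failure fairly well. Intermittent dialysis is given on some days only. Under the rule as written, the days between sessions earn credit whenever the patient is also off vasopressors and the ventilator, even though the kidneys have not recovered. Two patients with the same kidney failure can then score very differently because one is on intermittent and the other on continuous therapy, or because of local scheduling.

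Section 3.5.2 explains the -1 as a way to keep death distinct from organ dysfunction that persists. That reasoning presumes that persistent dysfunction scores near 0, which the literal rule does not deliver for intermittent dialysis.

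What is at stake is mainly the definition to be carried forward. Section 7.2 says the roll-in data are meant to allow rapid start of a much larger multi-center trial, and 7.3 plans analysis alongside a second center. If dialysis practice differed between centers (the documents do not say whether it does), the score would reflect that difference.

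**Working it through.** **The plan's own figure.** In the 3.5.2 example dysfunction resolves on day 9 and the patient is alive on day 28. With day 9 as the last supported day, the count is 28 - 9 = 19, which reproduces the stated 19. The example has a single unbroken period of support. Counting days without support and counting days after final resolution both give 19, so it does not settle the intermittent case.

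**Inputs for the illustration.**
- From the documents: the daily-receipt rule (1.0, 2.8.1, 3.5.2); the day-28 horizon; the first infusion day as day 0 (1.0); all patients on vasopressors at enrollment (2.5).
- Assumed: three dialysis sessions in every 7 days, on alternate days with one two-day gap, up to day 28; survival past day 28; for the comparison, continuous therapy on every day to day 28.

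**Ceiling.** Over days 1 to 28 there are 4 × 3 = 12 session days and 28 - 12 = 16 other days, whichever weekday the window starts on. Reaching 16 requires no vasopressor or ventilator on any non-dialysis day from day 1 on. For other frequencies of k sessions a week, the ceiling is 28 - 4k: 20 for k = 2, 16 for k = 3, 12 for k = 4, and 0 for daily therapy.

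**With other support as well.** If vasopressors or ventilation last through day v, only days v + 1 to 28 can be free.

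| Other support through | Days left | Sessions in those days | Scored as free | Daily continuous therapy |
|---|---|---|---|---|
| Day 3 | 25 | 10 to 11 | 14 to 15 | 0 |
| Day 7 | 21 | 9 | 12 | 0 |
| Day 14 | 14 | 6 | 8 | 0 |

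The ranges come from the weekday on which the window starts. The protocol does not say whether day 0 is in the window. Since patients enter on vasopressors, day 0 is normally not free, and a window of days 0 to 28 gives the same results. A window of days 0 to 27 gives 13 to 14, 11 to 12 and 7 to 8, with a ceiling of 15 to 16.

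**Under a bridging rule.** If every day from the first through the last session inside the window counts as supported, the days after the last session remain free. With a longest gap of two days, the last session falls on day 26, 27 or 28, which leaves 2, 1 or 0 free days. Carrying ongoing therapy through day 28 makes the score 0 in every case and equal to that for continuous therapy.

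**Death on day 28.** Take a patient whose last supported day is day 9 and who dies on day 28. Section 1.0 gives -1. Section 3.5.2 does not assign -1, so the day count stands: 28 - 9 = 19, or 18 if the day of death is not credited.

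**The case against.** The best case on the other side has four parts.

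- **Consequence here.** This is a single-arm, one-center study of up to 10 patients whose own outcomes are consent, compliance and coordinator time. A reader might infer that dialysis modality could bias the treatment effect in this study. It cannot: there is no control arm, so the comparison named in 7.1 has no second group. No sample size rests on the outcome either. This stands, and it limits the weight of the point.
- **Size.** A reader might take 16 of 28 as the score of a typical dialysis patient. The documents do not support that. Every patient enters on vasopressors, so 16 is a ceiling. The schedule is assumed, and nothing in the documents says how many patients would be dialysed. The gap from 0 is smaller than 16 in most courses, but it does not close.
- **The worked example.** A reader might infer that 3.5.2 contradicts its own rule. It does not, because 19 follows under either reading. The defect is a missing convention, not a contradiction.
- **Chronic dialysis.** It is tempting to ask for a score without the renal component for these patients. That would put them on a more lenient scale than everyone else, and nothing in the plan calls for it. Identifying them is enough.

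The day-28 wording is a separate matter. It is the only direct inconsistency in the text, and it lends no support to the dialysis argument.

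**Conclusion.** The point holds as a gap in an outcome definition. Under the text as written, days between intermittent dialysis sessions score as free while kidney failure continues. With three sessions a week to day 28 and survival past day 28, both assumed, the credit is about 14 to 15, 12 or 8 days when other support lasts through day 3, 7 or 14. The same failure on daily continuous therapy scores 0. A different session frequency changes these figures but not the direction.

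Independently, sections 1.0 and 3.5.2 score a death on day 28 differently, which needs no assumption to establish.

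Both are worth correcting now because the outcome is recorded in this study and intended for the main trial. Their effect on the conclusions of this roll-in is small.

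**What to change.** In 1.0, 2.8.1 and 3.5.2:

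- Count every calendar day from the first through the last renal replacement session as a day on renal replacement therapy, and continue that count through day 28 if therapy is still ongoing at day 28.
- State the -1 rule once, covering death on day 28 as well as before it, and use it throughout, including for ICU-free days in 2.8.2 and 3.5.3.
- Record whether the patient was on chronic dialysis before the septic episode. Under the bridging rule a patient dialysed throughout scores 0, and the flag lets the reader see how far such patients drive the results.

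The cost is a few sentences and one data field. The present rule already needs the dates on which renal replacement was given. For a patient discharged before day 28 on dialysis, status at day 28 has to be obtained; the telephone follow-up in 2.8.2 is described for mortality only, so it would need one more question. The downside is that affected patients score lower, and a patient with two separate courses of therapy loses credit for the interval between them. The change concerns scoring only, not how any treatment is given.
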